## ALGORITHM FOR TREATMENT EMERGENCE OF ADVERSE EVENTS:

START DATE	STOP DATE	ACTION
Known	Known Partial Missing	If start date < trial med start date or start date > trial med stop date +70 days, then not TEAE If start date >= trial med start date and start date <= trial med stop date +70 days, then TEAE
Partial, but known components show that it cannot be on or after trial med start date	Known Partial Missing	Not TEAE

Document: \\ieedc-nas01a\BIOSdata\Boehringer\_Ingelheim\BI\_695501\NVA96235\Biostatistics\Documentation\SAP\10  
 v1.0\BI\_1297.3\_SAP\_22JUN2016\_v1.0

Author: Version Number: 1.0  
 Version Date: 22JUN2016

Template No: CS\_TP\_BS016 – Revision 3  
 Effective Date: 01May2012

Reference: CS\_WI\_BS005

START DATE	STOP DATE	ACTION
Partial, could be on or after trial med start date	Known	
Impute start date as earliest possible date, (i.e. first day of month if day unknown or 1st January if day and month are unknown), except if only day is missing and month and year of start date are the same as for trial med start date or if day and month are missing and year of start date is the same as for trial med start date. In the later cases, the trial med start date will be used for the imputation.
 
If start date <= stop date, then :
 
 
If stop date < trial med start date, then not TEAE
 
If start date > trial med end date +70 days, then not TEAE
 
If stop date >= trial med start date and start date <= trial med end date +70 days, then TEAE
 
 
If start date > stop date, then :
 
Consider the start date as Missing and apply the algorithms for missing start date

	Partial	
Impute start date as above.
 
Impute stop date as latest possible date (i.e. last day of month if day unknown or 31st December if day and month are unknown), if not resulting in a date later than the date of subject's death. In the later case the date of death will be used for imputation.
 
If start date <= stop date, then :
 
 
If stop date < trial med start date, then not TEAE
 
If start date > trial med end date +70 days, then not TEAE
 
If stop date >= trial med start date and start date <= trial med end date +70 days, then TEAE
 
 
If start date > stop date, then :
 
Consider the start and stop dates as Missing and apply the algorithms for missing start date

	Missing	Assumed TEAE
Missing	Known	
If stop date < trial med start date, then not TEAE
 
If stop date >= trial med start date, then TEAE

	Partial	Impute stop date as latest possible date (i.e. last day of month if day unknown or 31st December if day and month

Document: \\ieedc-nas01a\BIOSdata\Boehringer\_Ingelheim\BI\_695501\NVA96235\Biostatistics\Documentation\SAP\10  
 v1.0\BI\_1297.3\_SAP\_22JUN2016\_v1.0

Author: Version Number: 1.0  
 Version Date: 22JUN2016

Template No: CS\_TP\_BS016 – Revision 3  
 Effective Date: 01May2012

Reference: CS\_WI\_BS005

START DATE	STOP DATE	ACTION
		are unknown), then: If stop date < trial med start date, then not TEAE If stop date >= trial med start date, then TEAE
	Missing	Assumed TEAE

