#### Serious adverse event

A SAE is defined as any AE which:

- results in death
- is life-threatening
- requires inpatient hospitalisation or prolongation of existing hospitalisation
- results in persistent or significant disability or incapacity
- is a congenital anomaly/birth defect
- or
- is to be deemed serious for any other reason if it is an important medical event when based upon appropriate medical judgment which may jeopardize the patient and may require medical or surgical intervention to prevent one of the other outcomes listed in the above definitions

Life-threatening in this context refers to an event in which the patient was at risk of death at the time of the event; it does not refer to an event that hypothetically might have caused death if more severe.

Every new occurrence of cancer will be reported as a SAE regardless of the duration between discontinuation of the drug and the occurrence of the cancer.

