## 5.3.7 Adverse event collection and reporting

### AE Collection

The following must be collected and documented on the appropriate eCRF by the Investigator:

- From signing the informed consent onwards through the Residual Effect Period (REP), all AEs (serious and non-serious), and AESIs
- After the individual patient's end of trial: the Investigator does not need to actively monitor for AEs but should only report relevant SAEs and relevant AESIs of which the Investigator may become aware of

The REP for BI 695501 is defined as 10 weeks after the last trial medication application. All AEs which occurred through the treatment phase and throughout the REP will be considered as on treatment. Events that occur after the REP will be considered as post-treatment events.

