### 16.1.1. ADVERSE EVENT SPECIFIC DERIVATION

#### 16.1.1.1. Treatment Emergent Adverse Event

Treatment-emergent adverse events (TEAEs) are defined as AEs that started or worsened in severity on or after the first dose of 1297.3 trial medication and prior to the last date of 1297.3 trial medication + 10 weeks inclusive.

Non-TEAEs will be classified as "Prior treatment" if AE start date is strictly prior the first injection date. Non-TEAEs will be classified as "Post treatment" if AE start date is strictly after the last injection date + 70 days.

See APPENDIX 2 for handling of partial dates for AEs. In the case where it is not possible to define an AE as treatment-emergent or not, the AE will be classified by the worst case; i.e. treatment-emergent.

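### The AE date table in SAP Appendix 2 has no end-of-window check for a partial start date with a missing stop date, so an ongoing event dated wholly after last dose + 70 days is counted as treatment-emergent

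*SAP*

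**What the plan says.** The AE table in SAP Appendix 2 sorts events first by how complete the start date is, then by stop date.

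- Known start, any stop (including missing): a start before first dose, or after "trial med stop date +70 days, then not TEAE".
- Partial start that must precede first dose, under the heading "Partial, but known components show that it cannot be on or after trial med start date": not a TEAE, whatever the stop date.
- Partial start under the heading "Partial, could be on or after trial med start date", with a known or partial stop: the start is imputed (in general to the earliest possible date), and the rule again ends with "trial med end date +70 days, then not TEAE".
- The same heading with a missing stop: the event is simply assumed to be a TEAE. No date is imputed and nothing is compared.

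The SAP body, section 16.1.1.1, puts an event in the post-treatment class "if AE start date is strictly after the last injection date + 70 days". It keeps the worst-case rule for one situation: "In the case where it is not possible to define an AE as treatment-emergent or not". Protocol 5.3.7 defines the residual effect period (REP) as the 10 weeks after last dose and adds: "Events that occur after the REP will be considered as post-treatment events".

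**The concern.** The heading of the partial-start block tests only the beginning of the window, and the missing-stop cell tests nothing further. Where the known part of the date already excludes the window at the early end, the table has a row that gives the right answer. There is no counterpart at the late end.

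The TEAE flag feeds the primary endpoint (patients with drug-related AEs during the treatment phase, SAP 16) and every treatment-emergent table. Events after the window can enter the data by three routes:

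- Protocol 5.3.6 says of cancer: "Every new occurrence of cancer will be reported as a SAE regardless of the duration between discontinuation of the drug".
- Protocol 5.3.7 has investigators report relevant SAEs and AESIs that they learn of after a patient's end of trial.
- Footnote 10 of the protocol Flow Chart counts AE capture from the EoT visit. In a patient who stops early, that visit may fall later than the last dose.

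A late event that is still ongoing has no stop date. If its onset is recorded only to the month or year, it falls into the unchecked cell.

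**Working it through.** No sample size or error rate is involved, and the plan states no figure to reproduce. The check is to run the table on dates.

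**Inputs.** Appendix 2 as described above. Illustrative dates (assumed, not from the documents): first dose 2016-03-01 and last dose on Day 337, which is 2016-03-01 + 336 days = 2017-01-31. The window ends at 2017-01-31 + 70 days = 2017-04-11, which is Day 407.

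**Step 1: one onset in June 2017, recorded four ways.**

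| Start recorded | Stop recorded | Appendix 2 result |
|---|---|---|
| 2017-06-15 | missing | not TEAE |
| 2017-06 | 2017-08-01 | not TEAE |
| 2017-06 | 2017-08 | not TEAE |
| 2017-06 | missing | **TEAE** |

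Only the last row disagrees. The onset month settles the class, since all of June lies after 11 April, so the worst-case condition of 16.1.1.1 is not met.

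**Step 2: add the sibling rows' check to the missing-stop cell.** All events are ongoing.

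| Start recorded | As written | With check |
|---|---|---|
| 2017-06 | TEAE | not TEAE |
| 2018 (year only) | TEAE | not TEAE |
| 2017-04 (straddles the end) | TEAE | TEAE |
| 2017-03 (inside) | TEAE | TEAE |
| 2017 (year only, could be inside) | TEAE | TEAE |
| 2016-02 (before first dose) | not TEAE | not TEAE |

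The check changes only events whose recorded period lies wholly after the window. Those that could fall inside it keep the worst-case treatment.

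**Step 3: compare with the rest of Appendix 2.** The algorithms for medications and for medical history and surgery meet the same pattern (partial start, missing stop). Both impute the start and assign post-treatment when it is late, with end of treatment as their limit. The AE cell therefore looks like an omission rather than a policy.

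**Step 4: size.** Protocol 7.7 expects 300 to 400 patients. The primary endpoint counts patients, so one wrongly added patient changes the proportion by at most 1/400 = 0.25 to 1/300 = 0.33 percentage points.

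For a rare category, suppose every patient contributes the full 407 days at risk:

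- Patient-years: 300 × 407/365.25 = 334 and 400 × 407/365.25 = 446.
- One added patient: 1000/334 = 3.0 to 1000/446 = 2.2 per 1000 patient-years.

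**Step 5: time at risk.** SAP 16.1.1.2 runs time at risk to the first qualifying AE. With an imputed onset of 2017-06-01, the misclassified patient would have 458 days, against 407 for an event-free completer. That is outside the risk period the rate is meant to describe.

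**The case against.** The strongest defence is that this hardly matters. Active AE collection ends with the REP. Later events reach the database only as cancers or as relevant SAEs and AESIs that the investigator happens to learn of. The EoT visit is meant to follow the last dose as soon as possible, so the early-stopper route should usually add little time. The bias runs in the direction that the SAP itself chooses when in doubt, no hypothesis is tested, and the listings show unimputed dates for TEAEs and non-TEAEs alike. All of this stands, and it limits the point to a minor correction. It does not make the cell right: the worst-case rule covers events that cannot be classified, and these can be.

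Three stronger readings might be inferred, and the documents do not support them.

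- *Late serious events are the ones most likely to have month-only onsets, so the error concentrates in rare tables.* Neither document gives a rate of partial dates. Protocol 5.3.7 asks for the onset of each AE and for SAE and AESI reports within 24 hours, which points the other way.
- *Every misclassified related event raises the primary proportion.* The endpoint counts patients. An event adds nothing if the patient already has a drug-related TEAE.
- *Time at risk cannot be computed for these patients.* SAP 6.1 sends durations with partial dates to the Appendix 2 imputations, and the start-date rule stands in the same block. The missing-stop cell merely fails to refer to it, which is a gap in wording.

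**Conclusion.** The cell is wrong as written. It classes as treatment-emergent an ongoing AE whose recorded month or year lies wholly after last dose + 70 days, against its own sibling rows, SAP 16.1.1.1 and protocol 5.3.7.

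The effect is small and goes one way. It needs a partial start, a missing stop and a recorded period entirely after the window. The number of such records is unknown and may be zero. To reach the primary endpoint, the event must also be marked drug-related or lack a causality entry (which SAP 16.1.2.2 counts as related), and the patient must have no other drug-related TEAE. The 0.25 to 0.33 percentage points is then the maximum per patient, assuming 400 to 300 treated. Outside the primary endpoint, a single such event could turn a zero into a one in a table such as malignancies (SAP 16.1.10.9).

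The assumption for an AE with both dates wholly missing is a different case. Its class cannot be determined, and that cell agrees with 16.1.1.1.

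**What to change.** Replace the action in the cell for partial start and missing stop with: impute the start date by the rule given for the known-stop row; if the imputed start is later than last dose + 70 days, class the event as not treatment-emergent (post-treatment); otherwise class it as treatment-emergent. Leave the cell for wholly missing start and stop dates unchanged.

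This wording also makes explicit that the imputed start is the one used for time at risk in SAP 16.1.1.2, in line with SAP 6.1.

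The cost is one table cell and about one line of code, to be done before database lock. The only downside is that a few events now counted by default would become post-treatment. They remain visible, because the listings in SAP 16.1 cover TEAEs and non-TEAEs.

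### SAP Appendix 2 can count an AE as treatment-emergent when its recorded stop month ended before the first dose, because the partial-start/partial-stop row discards both dates

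*SAP*

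**What the plan says.** The primary endpoint counts patients with drug-related treatment-emergent AEs (SAP Section 16). Section 16.1.1.1 defines these as AEs that "started or worsened in severity on or after the first dose of 1297.3 trial medication", up to 10 weeks after the last dose. It keeps the worst-case assignment for AEs whose status cannot be determined.

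Appendix 2 gives the rules for incomplete dates. The relevant row is headed "Partial, could be on or after trial med start date".

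- **Start.** The earliest possible date is used, with exceptions. One exception covers a start of which only the year is recorded, when the patient was first dosed in that same year. The SAP then directs: "In the later cases, the trial med start date will be used for the imputation".
- **Partial stop.** "Impute stop date as latest possible date (i.e. last day of month if day unknown".
- **Imputed start after imputed stop, stop partial.** "Consider the start and stop dates as Missing and apply the algorithms for missing start date".
- **Imputed start after imputed stop, stop known.** "Consider the start date as Missing and apply the algorithms for missing start date". Here the stop is kept.
- **Start missing, stop partial.** The stop is imputed to its latest possible date. If that date precedes first dose, the instruction ends "trial med start date, then not TEAE".
- **Start and stop both missing.** The AE is assumed to be treatment-emergent.

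**The concern.** In this situation the recorded dates do not conflict. The SAP creates the conflict itself by moving a year-only start forward to the first-dose date. Its conflict rule then discards the stop month, which is the one item that settles the question.

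The outcome also runs against the information available. With no start date at all and a pre-dose stop month, the AE is not treatment-emergent. Adding the start year turns it into a TEAE.

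Pre-dose AEs do reach the database. The protocol (Flow Chart footnote 10, Section 5.3.7) collects AEs from informed consent, which is given at Screening, nominally 14 days before first dose. Such an event arises on Trial 1297.2 medication, which for one of the three presentation groups was US-licensed Humira. If misclassified, it could enter the primary endpoint as an event on BI 695501 in this trial. SAP Section 16.1.2 plans a separate summary of Trial 1297.2 TEAEs in the 1297.3 screening phase, so the plan means to keep the two periods apart.

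**Working it through.** The plan states no figure to reproduce, because this is a deterministic date rule. The calendar dates below are assumptions.

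**1. One event under three rows.** Assume first dose on 5 Sep 2016. Nominal Screening is 14 days earlier, on 22 Aug 2016, so an AE that ended in August can lie in the collection window.

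| Recorded start | Recorded stop | Imputed start | Imputed stop | Rule applied | Result |
|---|---|---|---|---|---|
| 2016 | Aug 2016 | 5 Sep 2016 | 31 Aug 2016 | start > stop, both set missing | TEAE |
| 2016 | 31 Aug 2016 | 5 Sep 2016 | (known) | start > stop, only start set missing | not TEAE |
| missing | Aug 2016 | none | 31 Aug 2016 | stop before first dose | not TEAE |

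In the first line the AE ended at least 5 days before first dose.

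**2. Why no other clause in the row catches it.** Every start imputed in this row falls on or after first dose: it is either the first-dose date or the first day of a later month or year. If the imputed start is not after the stop, the stop is therefore also on or after first dose. The clause that returns not TEAE for a stop before first dose cannot operate here.

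**3. Which records are affected.** Enumerate all year-only and month-year start/stop pairs for 2015 to 2017, with first dose on the 15th of each month of 2016. A pair is mutually consistent if the earliest possible recorded start is not after the latest possible stop. The consistent pairs that reach the conflict rule are exactly those with a year-only start in the first-dose year and a stop in an earlier month of that year. There are none for a January first dose, 5 for June and 11 for December: 0 + 1 + … + 11 = 66. In all 66 the AE ended before first dose, and in all 66 the rule returns TEAE.

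**4. How often the screening window allows it.** The stop must fall at or after consent, so the 14-day window has to cross a month boundary within one calendar year. That happens when first dose is on day 1 to 14 of any month except January: 14 × 11 = 154 of 366 dates in 2016, or 42%. Across all 2016 first-dose dates there are 2,018 consistent pairs of first-dose date and earlier stop month. Only 154 of them (7.6%) fit inside the screening window. A year-only onset and a month-year stop are needed as well.

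**5. Effect on the primary proportion.** One patient is 100/400 = 0.25 points at N = 400 and 100/300 = 0.33 points at N = 300, using the protocol's anticipated 300 to 400 patients.

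**6. Effect of discarding only the start in every conflict.** In the step 3 enumeration the conflict rule is reached 6,656 times. Discarding only the start everywhere would move 4,408 of these to not TEAE. Of the 4,408, 66 are the consistent records, and in 3,964 the recorded start lies wholly after first dose. The other 378 are contradictory records whose recorded start period contains the first dose (66 + 3,964 + 378 = 4,408). These are counts of combinations, not expected frequencies.

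**The case against.** The best defence is that discarding both dates suits records that really do conflict. Take first dose on 15 Sep 2016, start Nov 2016 and stop Jun 2016. The onset is recorded after first dose and the stop may be a typing error. The present rule keeps this AE as treatment-emergent, in line with the worst-case principle. Discarding only the start in every conflict would drop it from the safety endpoint. This objection stands, and it limits the remedy. It does not defend the result for consistent records, because the worst-case principle covers only AEs whose status cannot be determined, and here it can be. Worsening does not rescue the result either: under SAP Section 16.1 a worsened AE becomes a new entry, so a record that stopped before first dose cannot have worsened on treatment.

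It is also fair to say that the trial is descriptive, that the error over-counts and does not hide events, and that the unreachable clause may simply be template text, since it also sits in the known-stop row. These points bear on importance and on intent, not on the logic.

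A reader might infer that every AE with a pre-dose stop month is misclassified. The documents do not support that. A start whose known parts place it before first dose is not treatment-emergent, and neither is a missing start with a pre-dose partial stop. A reader might also take the 66 of 66 as a sign of frequent error. It shows only that the rule is always wrong for consistent records that reach it. With first dose on the 15th, none of those 66 lies inside a 14-day screening window.

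**Conclusion.** As written, the partial-start/partial-stop row gives a wrong classification for a narrow, well-defined kind of record. It is inconsistent with two neighbouring rows, and nothing elsewhere in the SAP corrects it. It feeds the derivation of the primary endpoint, in the direction of over-counting.

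The practical size is small. A record must combine a year-only onset, a month-year stop and a screening window that crosses a month boundary within one year (about 42% of first-dose dates, assuming 14 days). The figure of 0.25 to 0.33 percentage points is a ceiling per affected patient. It is reached only if the AE is drug-related or has missing relatedness (counted as related under SAP Section 16.1.2.2), and the patient has no other drug-related TEAE. The documents do not support reading this as a material bias in the primary result. It is a minor correction, worth making before programming.

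**What to change.** In the partial-start/partial-stop row of the Appendix 2 TEAE algorithm, split the case where the imputed start falls after the imputed stop:

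- **Recorded parts mutually consistent** (earliest possible recorded start not after latest possible stop): set only the start to missing, keep the imputed stop, and apply the missing-start/partial-stop rule. A stop before first dose then gives not TEAE; any other stop gives TEAE.
- **Recorded parts contradictory** (for example, recorded start month after recorded stop month): keep the present rule, with both dates missing and TEAE assumed, or query the record. AEs with a recorded post-dose onset then stay in the safety endpoint.

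With this change the 5 Sep 2016 example becomes not TEAE, and the Nov/Jun example stays TEAE unless a query changes its dates. The cost is a few words in one table cell and one extra condition in the code, with no new data. The known-stop row already discards only the start, including for contradictory records. Whether it should carry the same condition can be decided at the same time.

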## ALGORITHM FOR PRIOR / CONCOMITANT MEDICATIONS:

Partial date to be imputed as:

Start date	Earliest possible date	first day of month if day unknown or 1 st January if day and month are unknown
Stop date	Latest possible date	last day of month if day unknown or 31 st December if day and month are unknown

General rules:

- If stop date < trial med start date, assign as prior
- If stop date >= trial med start date and start date <= end of treatment, assign as concomitant
- If stop date >= trial med start date and start date > end of treatment, assign as post Treatment

If Missing stop date: (Rules 2)

- If stop date is missing could never be assumed a prior medication
- If start date <= end of treatment, assign as concomitant
- If start date > end of treatment, assign as post treatment

If Missing Start date: (Rules 3)

- If stop date < trial med start date, assign as prior
- If stop date >= trial med start date, assign as concomitant
- Cannot be assigned as 'post treatment'

START DATE	STOP DATE	ACTION
Known	Known	General rules
	Partial	General rules
	Missing	Rules 2

Document: \\ieedc-nas01a\BIOSdata\Boehringer\_Ingelheim\BI\_695501\NVA96235\Biostatistics\Documentation\SAP\10  
v1.0\BI\_1297.3\_SAP\_22JUN2016\_v1.0

Author: Version Number: 1.0  
Version Date: 22JUN2016

Template No: CS\_TP\_BS016 – Revision 3  
Effective Date: 01May2012

Reference: CS\_WI\_BS005

START DATE	STOP DATE	ACTION
Partial	Known	General rules
	Partial	General rules
	Missing	Rules 2
Missing	Known	Rules 3
	Partial	Rules 3
	Missing	Assign as concomitant

---

Document: \\ieedc-nas01a\BIOSdata\Boehringer\_Ingelheim\BI\_695501\NVA96235\Biostatistics\Documentation\SAP\10  
 v1.0\BI\_1297.3\_SAP\_22JUN2016\_v1.0

Author: Version Number: 1.0  
 Version Date: 22JUN2016

Template No: CS\_TP\_BS016 – Revision 3  
 Effective Date: 01May2012

Reference: CS\_WI\_BS005

---

